##### Observation period and follow-up period by 30 days:

Adverse events

Priority survey items:

Cardiovascular adverse events

Anticholinergic-related adverse events

Asthma related death/hospitalization/intubation

Safety laboratory test (if corresponding AEs are reported)

See [ANNEX 3](#) for more details.

#### **9.4 DATA SOURCES**

Case Report Forms (CRFs) for individual patients will be provided by the sponsor via the Electronic Data Capture (EDC) system.

One case book is used. Book 1 is for baseline, Week 4 and Week 12.

Data is to be transmitted immediately after being entered into the eCRF at 12 weeks after the start of treatment or at discontinuation. When any adverse events occur, the data should be immediately entered into eCRF and transmitted.

#### **9.5 STUDY SIZE**

It is planned to enroll 180 patients with mild to moderate persistent asthma to ensure the number of 150 patients as safety analysis set at least.

150 (safety set)

150 patients will be set as a safety analysis set. The main ADR (about 2.0%) in clinical trials were asthma (1.8%), dysphonia (1.8%) and dry mouth (1.8%). With 150 patients, the incidence of the main adverse events would be evaluated.

#### **9.6 DATA MANAGEMENT**

Data is gathered by the EDC system provided by external vendor below.

Table 9.6: 1

	Contract research organizations 1	Contract research organizations 2
Name		

#### **9.7 DATA ANALYSIS**

This is a non-interventional, observational study to collect new real-world data (i.e., data under routine medical practice) on safety and effectiveness of Spiriva Respimat treatment in patients. Analyses are descriptive in nature including means, standard deviation, Q1, medians,

Q3, frequency and percentages. For safety outcomes, incidence rates with corresponding 95% confidence intervals will also be calculated. No confirmatory statistical testing is foreseen in this study.

Per local regulation, any patient who meets one of the following criteria is treated as ineligible for all analyses:

- No safety observation was documented after registration
- No required registration procedure was followed
- No valid site contract was available

### **9.7.1 Main analysis**

The analysis of outcome events will include all patients registered in the study and receiving the Spiriva Respimat treatment. All outcome events are based on reported AE data which will be handled according to BI standards.

The safety analysis will include all patients registered in the study and receiving the Spiriva Respimat treatment. In general, safety analyses will be descriptive in nature, will be based on BI standards, and will focus on ADRs related to the Spiriva Respimat treatment.

AEs will be coded using the current version of the Medical Dictionary for Regulatory Activities (MedDRA) and will be based on the concept of treatment emergent AEs. To this end, all AEs occurring between the first intake of Spiriva Respimat prescribed at baseline visit and within 30 days (inclusive) after the last intake will be considered 'treatment emergent'. An AE is considered to be ADR if either the physician who has reported the AE or the sponsor assesses its causal relationship as 'related'.

The frequency of AEs/ADRs will be tabulated by system organ class and preferred term for overall and for subgroups based on the important baseline characteristics.

No imputation is planned for missing AE data except for missing onset dates which will be handled according to BI standard.

### **9.7.3 Interim analyses**

Several interim analyses will be performed for the purpose of creating periodic safety update reports to the local authority ([see 6. MILESTONES](#)).

## **9.8 QUALITY CONTROL**

All processes are conducted according to GPSP SOPs and GPSP working instruction. Appropriate records and documents are stored based on the GPSP SOPs and these processes are checked by internal self-check.

## **9.9 LIMITATIONS OF THE RESEARCH METHODS**

No randomized assignment of patients to the survey is implicated. This may induce selection bias. The site will be nominated by the availability of conducting the study with a peak flow meter, and might have a more intensive observation compared with the non-selected site.

## **9.10 OTHER ASPECTS**

### **9.10.1 Data quality assurance**

This PMS is to be conducted in accordance with both the in-house PMS SOP and working instructions which are in compliance with GPSP. This study should be conducted in compliance with SOP 001-MCS-90-118.

### **9.10.2 Study records**

Case Report Forms (CRFs) for individual patients will be provided by the sponsor, via EDC.

#### **9.10.2.1 Source documents**

Source documents provide evidence for the existence of the patient and substantiate the integrity of the data collected. Source documents are filed at the investigator's site.

Data entered in the eCRFs that are transcribed from source documents must be consistent with the source documents or the discrepancies must be explained. The investigator may need to request previous medical records or transfer records, depending on the study; also current medical records must be available.

For eCRFs all data must be derived from source documents.

#### **9.10.2.2 Direct access to source data and documents**

Direct access to source data and documents for PMS is not allowed in Japan.

### **9.10.3 Completion of study**

When the study is completed, the investigator should inform the head of the study site of the completion in writing, and the head of the study site should promptly inform the IRB and sponsor of the completion in writing.

## **10. PROTECTION OF HUMAN SUBJECTS**

There is no regulation or requirement for ensuring the well-being and rights of participants in a non-interventional observational study.

### **10.1 STUDY APPROVAL, PATIENT INFORMATION, AND INFORMED CONSENT**

The review by IRB is not mandatory for conducting PMS in Japanese GPSP. The sponsor will enter into a contract with a representative (e.g., head of hospital) in accordance with GPSP. Written informed consent prior to patient participation in the trial is not a regulatory or legal requirement in accordance with GPSP.

### **10.2 STATEMENT OF CONFIDENTIALITY**

Individual patient medical information obtained as a result of this PMS is considered confidential and disclosure to third parties is prohibited with the exceptions noted below. Patient confidentiality will be ensured by using patient identification code numbers.

Data generated as a result of the PMS needs to be available for inspection on request by the regulatory authorities.

## **11. MANAGEMENT AND REPORTING OF ADVERSE EVENTS/ADVERSE REACTIONS**

Procedures for the collection, management and reporting of individual cases of adverse events/adverse reactions (see [001-MCS-05-501-RD-01](#) for collection requirements) and of any new information that might influence the evaluation of the benefit-risk balance of the product while the study is being conducted.

### **11.1 DEFINITIONS OF ADVERSE EVENTS**

#### Adverse event

An adverse event (AE) is defined as any untoward medical occurrence in a patient or clinical investigation subject administered a medicinal product and which does not necessarily have a causal relationship with this treatment. An adverse event can therefore be any unfavourable and unintended sign (e.g. an abnormal laboratory finding), symptom, or disease temporally associated with the use of a medicinal product, whether or not considered related to the medicinal product.

#### Adverse reaction

An adverse reaction is defined as a response to a medicinal product which is noxious and unintended. Response in this context means that a causal relationship between a medicinal product and an adverse event is at least a reasonable possibility. Adverse reactions may arise from use of the product within or outside the terms of the marketing authorisation or from occupational exposure. Conditions of use outside the marketing authorization include off-label use, overdose, misuse, abuse and medication errors.

#### Serious adverse event

A serious adverse event is defined as any AE which

- results in death,
- is life-threatening,
- requires in-patient hospitalization, or
- prolongation of existing hospitalisation,
- results in persistent or significant disability or incapacity, or
- is a congenital anomaly/birth defect

Life-threatening in this context refers to a reaction in which the patient was at risk of death at the time of the reaction; it does not refer to a reaction that hypothetically might have caused death if more severe.

Medical and scientific judgement should be exercised in deciding whether other situations should be considered serious reactions, such as important medical events that might not be immediately life threatening or result in death or hospitalisation but might jeopardise the patient or might require intervention to prevent one of the other outcomes listed above. Examples of such events are intensive treatment in an emergency room or at home for allergic bronchospasm, blood dyscrasias or convulsions that do not result in hospitalisation or

development of dependency or abuse. Any suspected transmission via a medicinal product of an infectious agent is also considered a serious adverse reaction.

An AE which possibly leads to disability will be reported as an SAE.

No AESIs have been defined for this study.

## **11.2 ADVERSE EVENT AND SERIOUS ADVERSE EVENT COLLECTION AND REPORTING**

The investigator shall maintain and keep detailed records of all AEs in their patient files.

### Collection of AEs

The study design is of non-interventional nature and the study is conducted within the conditions of the approved marketing authorisation. Sufficient data from controlled interventional trials are available to support the evidence on the safety and efficacy of the studied BI drug. For this reason the following AE collection and reporting requirements have been defined.

The following must be collected by the investigator in the eCRF. When any adverse events occur, the data should be immediately entered into eCRF and transmitted. :

- all adverse drug reaction (ADRs) (serious and non-serious),
- all AEs with fatal outcome,

All ADRs, including those persisting after study completion must be followed up until they are resolved, have been sufficiently characterized, or no further information can be obtained.

The investigator carefully assesses whether an AE constitutes an ADR using the information below.

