### ANNEX 3. FLOW CHART OF VARIABLES

#### 1. Observation period

Item \ Time	Observation period 		
	Before first administration of Spiriva Respimat	4W	12W (or at discontinuation)
Patient registration	X 		
Patient demographics	X		
Administration of Spiriva Respimat	X (to be recorded throughout the observation period)		
Medical history/baseline conditions	X		
Previous/concomitant therapies	X (to be recorded throughout the observation period)		
Pulmonary function test			
FEV 1	(X)	(X)	(X)
FVC	(X)	(X)	(X)
PEFR 	(X)	(X)	(X)
Asthma severity	X		
Asthma Control Status	(X)	(X)	(X)
QOL (ACQ 6 score)	(X)	(X)	(X)
Adverse events	X (to be recorded throughout the observation period)		
Laboratory tests  associated with AE		(X)	
EDC transmitted time 		X	

(X): If applicable

- 1: Time points during the observation period are approximate. Collected data should be reported as of the closest available visit.
- 2: Patients administered Spiriva Respimat will be registered within 14 days from whenever the day of first administration is possible.
- 3: PEFR is defined as the mean of the PEFR values of the 7 days before each visit.
- 4: When laboratory related AE is reported, Laboratory tests associated with AE are reported.
- 5: eCRF (electronic case report form): Data are to be transmitted immediately after being entered into the eCRF at 12 weeks after the start of treatment or at discontinuation. In case of occurrence of any adverse events, the data should be immediately entered into the eCRF and transmitted.

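### Protocol 11.2 requires only ADRs and fatal AEs in the eCRF, but 9.3.3, Annex 3 and the SAP tables set no such limit, so AE and serious-AE tables could be incomplete without saying so

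*Protocol*

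**What the plan says.** **Protocol 11.2, Collection of AEs.** The section argues that controlled trials already supply enough safety evidence and that the collection rules follow from this. The rule then opens: "The following must be collected by the investigator in the eCRF. When any adverse events occur, the data should be immediately entered into eCRF". Two items follow: "all adverse drug reaction (ADRs) (serious and non-serious" and "all AEs with fatal outcome". The section also asks investigators to keep records of all AEs in the patient files.

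**Protocol 9.3.3.** Under "Observation period and follow-up period by 30 days" the section lists adverse events and three priority survey items: cardiovascular events, anticholinergic-related events, and "Asthma related death/hospitalization/intubation". None is conditioned on causality.

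**Protocol 9.4.** "When any adverse events occur, the data should be immediately entered into eCRF and transmitted".

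**Protocol Annex 3.** The adverse-event row reads "X (to be recorded throughout the observation period". Footnote 5, attached to the row on EDC transmission time, reads "In case of occurrence of any adverse events, the data should be immediately entered into the eCRF and transmitted".

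**SAP 7.8.1.** AEs and ADRs are tabulated by system organ class and preferred term, serious AEs have their own table, and priority survey items are summarised separately. CRF data are first merged with AE data from a second source, the perceive system. Both Protocol 9.7.1 and SAP 7.8.1 count an AE as an ADR if either the reporting physician or the sponsor considers it related.

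**The concern.** The collection rule and the planned tables do not have the same scope. An event that is non-fatal and judged unrelated by the investigator is not on the 11.2 list, even if it is serious, such as a hospitalisation. It does belong in an AE table or a serious-AE table as the SAP describes them.

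If sites follow the list, such events need not reach the eCRF. If some sites follow the list and others enter every AE, capture differs by site for reasons unrelated to the drug. In both cases the reader of a table headed as AEs or serious AEs would not know that part of the class was never required.

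Recovery would be awkward. The events should be in the patient files, but Protocol 9.10.2.2 rules out direct access to source data, so the sponsor could learn of them only by asking sites.

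**Working it through.** The plan states no figure on this point, so the check is mainly a comparison of the texts.

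**1. Which passages set scope?**

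| Place | Scope for AEs | Clear or open |
|---|---|---|
| Protocol 11.2, two-item list | ADRs and fatal AEs | Clear |
| Protocol 11.2, sentence before the list | Any AE | Open: scope, or timing of entry |
| Protocol 9.4 | Any AE | Open: same sentence, after a rule on when routine data are sent |
| Annex 3, footnote 5 | Any AE | Open: attached to transmission time |
| Protocol 9.3.3 | AEs and priority items | No causality limit |
| Annex 3, adverse-event row | AEs | No causality limit |
| SAP 7.8.1 tables | AEs, serious AEs, priority items | No limit to ADRs or fatal events |

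**2. Try both readings of the three open sentences.** If they set scope, the two-item list has no function. If they set only timing, the list governs, but 9.3.3, the Annex 3 row and the SAP tables remain wider than it. Neither reading removes the mismatch.

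**3. Which tables are exposed?** 9.3.3 puts adverse events and priority items under one heading. A site that treats 11.2 as overriding 9.3.3 therefore does so for the AE, serious-AE and priority-item tables alike.

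**4. What reaches the primary outcome?** Every ADR judged by the investigator is on the list, and so is every fatal AE. What is left is a non-fatal AE that the investigator calls unrelated and the sponsor would have called related. If it is never entered and does not arrive by another route, the sponsor cannot assess it. The number of such events may be zero.

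**5. Scale only.** Inputs: a safety set of 150 and enrolment of 180 (Protocol 9.5); about 25 sites (Protocol 9.2.1).

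- One patient in the primary outcome: 1/150 = 0.67 percentage points, or 1/180 = 0.56 if all enrolled patients are analysed.
- One site following the list, assuming equal enrolment: 150/25 = 6 patients, and 6/150 = 4%. With 180 patients, 180/25 = 7.2, and 7.2/180 = 4%.
- Number of such sites: unknown, 0 to 25, hence 0 to 150 patients (0% to 100%) under the narrower rule.

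These are patients exposed to a rule, not missing events. A count of missing events would need an all-AE or SAE rate and the share judged unrelated. Protocol 9.5 gives only ADR rates.

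**The case against.** The strongest reply is that there is no contradiction, only a deliberate restriction stated in the section that owns the topic. Much of this stands:

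- 11.2 gives a rationale for the restriction. Its later paragraphs speak of reportable AEs, which implies that some AEs are not. Item 3.5 of the ENCePP checklist in Annex 2 names section 11 as the place where AE collection is described.
- The any-AE sentences in 9.4, 11.2 and footnote 5 can fairly be read as saying when AE data are sent, not which AEs are due.
- Protocol 9.3.2.1 names AEs of any seriousness as a safety parameter. That concerns seriousness, not causality, and is compatible with the list. Protocol 9.7.1 says that the safety analysis focuses on ADRs.
- The list is a required minimum and does not forbid entering other AEs. It ends in a comma, so an item lost when the text was extracted cannot be excluded.
- The perceive system, or the external collection document to which section 11 points, may bring in the missing events.

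A reader might therefore go too far in the other direction and infer that the any-AE rule is the settled one and that 11.2 is simply a mistake to be widened. The documents do not support that, because the restriction has a stated reason.

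The reply still leaves a gap. A deliberate restriction does not explain why 9.3.3 and the Annex 3 row carry no limit, or why the SAP tables do not mention one. A minimum that sites may exceed at will is itself a source of uneven capture. The scope of the second source and of the external document is not visible, so neither can be counted on to close the gap or assumed to leave it open.

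**Conclusion.** The point holds as a mismatch of scope between the required eCRF collection in 11.2 and the AE variables and tables elsewhere. It should be fixed. Confidence is high for the mismatch in the text and low for its consequence, which depends on how sites read the protocol and on what the second source holds.

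The size for the AE, serious-AE and priority-item tables cannot be derived and could be nil. The 4% per site rests on assumed equal enrolment and shows scale only.

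A reader might also infer that the primary ADR frequency is undercounted. The documents do not show this: investigator-judged ADRs are required under either reading, and only non-fatal, sponsor-only ADRs are exposed. The analysis is descriptive, so no test or power statement is affected.

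**What to change.** State one AE scope and use it throughout. The sponsor should choose between:

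- **(a) Keep the 11.2 restriction.** Align 9.3.3, 9.4, the any-AE sentence in 11.2, and the Annex 3 row and footnote 5 with it. Title and footnote the SAP AE, serious-AE and priority-item tables by what was actually collected, including what the second source adds.
- **(b) Collect all AEs.** Change the 11.2 list and its rationale to say so, and instruct sites.

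In both cases, add a sentence to SAP 7.8.1 saying which AEs the perceive system contains. If an instruction would come too late to change what sites enter, the titles and footnotes under (a) are still needed.

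Cost: (a) takes wording edits at five protocol places plus table titles and footnotes. (b) takes fewer text edits, a site instruction, and some extra AE entries on the existing eCRF.

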### Causal relationship of adverse event

The definition of an adverse reaction implies at least a reasonable possibility of a causal relationship between a suspected medicinal product and an adverse event. An adverse reaction, in contrast to an adverse event, is characterised by the fact that a causal relationship between a medicinal product and an occurrence is suspected.

Medical judgment should be used to determine the relationship, considering all relevant factors, including pattern of reaction, temporal relationship, de-challenge or re-challenge, confounding factors such as concomitant medication, concomitant diseases and relevant history.

Arguments that may suggest **a reasonable causal relationship** could be:

- The event is **consistent with the known pharmacology** of the drug
- The event is known to be caused by or **attributed to the drug class**.
- A **plausible time to onset of the event** relative to the time of drug exposure.
- Evidence that the **event is reproducible** when the drug is re-introduced

- **No medically sound alternative etiologies** that could explain the event (e.g. preexisting or concomitant diseases, or co-medications).
- The event is typically **drug-related and infrequent in the general population** not exposed to drugs (e.g. Stevens-Johnson syndrome).
- An indication of dose-response (i.e. greater effect size if the dose is increased, smaller effect size if dose is diminished).

Arguments that may suggest that there is **no reasonable possibility of a causal relationship** could be:

- No plausible time to onset of the event relative to the time of drug exposure is evident (e.g. pre-treatment cases, diagnosis of cancer or chronic disease within days/weeks of drug administration; an allergic reaction weeks after discontinuation of the drug concerned)
- Continuation of the event despite the withdrawal of the medication, taking into account the pharmacological properties of the compound (e.g. after 5 half-lives). Of note, this criterion may not be applicable to events whose time course is prolonged despite removing the original trigger.
- Additional arguments amongst those stated before, like alternative explanation (e.g. situations where other drugs or underlying diseases appear to provide a more likely explanation for the observed event than the drug concerned).
- Disappearance of the event even though the study drug treatment continues or remains unchanged.

#### Intensity of adverse event

The intensity of the AE should be judged based on the following:

Mild:	Awareness of sign(s) or symptom(s) which is/are easily tolerated
Moderate:	Enough discomfort to cause interference with usual activity
Severe:	Incapacitating or causing inability to work or to perform usual activities

#### Pregnancy:

In rare cases, pregnancy might occur in a study. Once a subject has been enrolled into the study, after having taken Spiriva Respimat, the investigator must report any drug exposure during pregnancy, which occurred in a female subject or in a partner to a male subject to the Sponsor by means of Part A of the Pregnancy Monitoring Form. The outcome of the pregnancy associated with the drug exposure during pregnancy must be followed up and reported by means of Part B of the Pregnancy Monitoring Form.

In the absence of a reportable AE, only the Pregnancy Monitoring Form must be completed, otherwise the NIS AE form is to be completed and forwarded as well as soon as possible.

#### Information required

For each reportable adverse event, the investigator should provide the information requested on the appropriate (e)CRF pages.

#### Reporting of related Adverse Events associated with any other BI drug

The investigator is encouraged to report all adverse events related to any BI drug other than Spiriva Respimat, according to the local regulatory requirements for spontaneous AE reporting at the investigator's discretion by using the locally established routes and AE report forms. The term AE includes drug exposure during pregnancy, and, regardless of whether an AE occurred or not, any abuse, off-label use, misuse, medication error, occupational exposure, lack of effect, and unexpected benefit.

